We will test the hypotheses related to examining effectiveness of participation in the RTS in leading to reductions in CSEC perpetration (primary outcome), as well as reductions in CSEC victimization and TDV and SV victimization and perpetration and increases in bystander intervention in CSEC situations (secondary outcomes). To improve the rigor of analyses for Aim 2a, we will use propensity-score analysis to reduce the impact of selection bias, and latent constructs, when possible, to reduce measurement error, reduce paths and variables, and increase statistical power (MacCallum et al., 1996). This approach produces rigorous estimates of causal effects within the context of quasi-experimental designs when random assignment is not possible by controlling confounders, including selection effects¹⁴⁴. This approach will use four analytic steps: (1) estimate propensity scores in a separate analysis, (2) use the propensity scores to adjust for confounding, (3) assess balance, and (4) estimate the propensity score-adjusted treatment effects (Lanza et al., 2013). In step 1, to estimate the propensity score, we will consider all pertinent confounders and covariates (see Measurement Table 3). This step will use logistic regression of condition on the potential confounders to obtain each student's propensity score. All measured confounders that are predictive of selection into the experimental conditions and the outcomes will be included in the propensity model. Standardized mean differences in covariate values across treatment and comparison conditions will be used to determine the final set of confounders to include in estimating the propensity score. In step 2, an initial treatment effect model is estimated that adjusts for confounding using the propensity score. We will use inverse probability weighting (IPTW) to adjust for confounding. The standardized mean differences between experimental groups are computed on the weighted sample included the IPTW-adjusted propensity score (Step 2). If IPTW does not provide optimal balance, then other methods will be considered (e.g., matching). Then Step 3 is used to determine balance on the potential confounders included in the propensity score across the experimental groups. The goal is to determine whether there are any differences remaining on the confounders between experimental groups (balance = standardized mean differences $< |0.2|$ after adjustment). Confounders will be adjusted and the propensity score model (Step 1) will be re-estimated until balance is reached. Once balance is determined, the outcome analysis will be conducted in Step 4 via SEM. The experimental effect of interest will be the Average Treatment Effect (ATE), which is the population-level average effect of condition on the primary and secondary outcomes as detailed in the logic model. The effects of interest quantified are differences between experimental conditions at post-test and follow-up on outcomes (for continuous measures), the propensity score as a covariate. These effects indicate whether the outcomes in the experimental condition differ significantly from those in the comparison condition. At post-test and follow-up, we expect the difference between the experimental conditions to be significantly greater than zero, reflecting better outcomes for those in the RTS program as compared to those in the wait-list condition, after adjusting for the

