
propensity score. For categorical variables, logistic regression will be used to examine differences in prevalence by condition. The experimental condition is the independent variable in these models. Multilevel modeling is not possible given the small number of schools; thus, school will be included as a covariate. Classroom will be used as a cluster variable to adjust the standard errors for nesting. Models for Step 4 will be evaluated for overall model fit via χ^2 statistic, RMSEA :s .08, SRMR :s .10, and CFI \geq .90. We will evaluate our hypotheses across several indicators, including significance (p), confidence intervals, and the standardized difference between groups (d), as well as the directionality of included path coefficients, and odds ratios.

Mediation and Moderation Analyses (Aim 2b).

We will assess mediators (e.g., perceptions of norms intolerant of CSEC) and demographic moderators (e.g., gender) of program effectiveness, including the propensity score and school as covariates in all models. To test for mediation, we used the product of coefficients method using bias-corrected bootstrapping with 1000 resamples to calculate the confidence intervals¹⁴⁵ (MacKinnon, 2012). For our moderators (e.g., age, gender, racial groups, sexual orientation), we will estimate structural equation multiple group models, first allowing estimation of the path coefficients to vary freely across groups, and then constraining paths to be equal when a structural path coefficient of interest was significant for one group and not the other group. We will conduct model comparisons using the chi-square (χ^2) difference test (i.e., χ^2 , $p < .05$ indicating moderation).

Aim 2c. Descriptive statistics will be used to examine the extent to which sessions were delivered with fidelity. Process observations will be analyzed using thematic analysis as described above for Aim 1b.

Aim 2d. Descriptive statistics will be used to examine the frequency of responses to close-ended questions (e.g., To what extend did you like the session today?). Open-ended questions will be analyzed using thematic analysis as described above for Aim 1b.

Aim 2e. Interview data will be analyzed using thematic analysis as described above for Aim 1b.

Aim 2f. The purpose of this aim is to determine costs associated with the program implementation to inform future economic evaluation of the RTS. The process for documenting costs are described in Section C.18.

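### Aim 2a Step 4 does not name the baseline outcome as a covariate; it probably enters the propensity score, but the text does not guarantee it, so naming it is a cheap safeguard

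*SAP*

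**What the plan says.** SAP, Outcome Analyses (Aim 2a), sets out four propensity-score steps.

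- **Step 1, candidates:** "we will consider all pertinent confounders and covariates (see Measurement Table 3". That table is not among the documents.
- **Step 1, entry rule:** "All measured confounders that are predictive of selection into the experimental conditions and the outcomes will be included in the propensity model".
- **Step 1, final selection:** "Standardized mean differences in covariate values across treatment and comparison conditions will be used to determine the final set of confounders". No cut-off is given.
- **Step 3, balance:** the purpose is to "determine balance on the potential confounders included in the propensity score across the experimental groups", with the limit "balance = standardized mean differences $< |0.2|$ after adjustment".
- **Step 4, outcome model:** the effects for continuous measures are "differences between experimental conditions at post-test and follow-up on outcomes (for continuous measures), the propensity score as a covariate". For the rest, "For categorical variables, logistic regression will be used to examine differences in prevalence by condition". School is a further covariate, and standard errors are clustered on classroom.

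The baseline outcome is not named in Step 4. Two other places in the SAP bear on this. The Aim 1e pilot analysis is an ANCOVA that explicitly adjusts for it, and Preliminary Analyses (Aims 2a and 2b) says all enrolled cases have baseline data. Power Analyses, Aim 2a, gives a minimum detectable effect of d = .06 for bystander action and the intermediary outcomes. For the primary outcome, CSEC perpetration, it gives odds ratios of .49 (1% incidence) to .75 (5%), with 7,241 students.

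**The concern.** Students are not randomised, so a baseline difference between conditions in the outcome itself is the most obvious confounder. The larger confirmatory analysis is less explicit about it than the pilot.

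One route through the steps would leave it unadjusted. If the SMD-based selection in Step 1 dropped a baseline outcome, Step 3 would not check its balance and Step 4 would not adjust for it. No later step would show the omission. With 7,241 students the trial is powered for very small effects, so even a modest residual imbalance could matter.

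**Working it through.** **Inputs from the SAP:** N = 7,241; power .80; alpha .05 (sidedness not stated); minimum detectable d = .06; primary-outcome OR .75 at 5% incidence. **Assumed:** 1:1 allocation in Aim 2a; r (baseline to follow-up correlation) of .3 to .5; phi (the same for a binary outcome) of .2 to .3; SMDs of .10 and .19. The documents give none of these. Clustering is ignored unless stated.

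**1. The plan's own figure.** SE of d = 2/√7,241 = .0235. One-sided: (1.645 + .842) × .0235 = .058. Two-sided: (1.960 + .842) × .0235 = .066. Two-sided with a covariate correlated .41 with the outcome: .066 × √(1 − .41²) = .060. The stated .06 therefore fits either a one-sided test or an ANCOVA with a moderately correlated covariate. The SAP calls the routine ANCOVA but names no covariate.

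**2. Baseline outcome in neither the score nor Step 4.** Bias ≈ SMD × r, if the scored confounders are unrelated to it.

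| SMD | r = .3 | r = .5 | r needed to reach .06 |
|---|---|---|---|
| .10 | .030 | .050 | .06/.10 = .60 |
| .19 | .057 | .095 | .06/.19 = .32 |

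A simulation (N = 7,241, four other confounders in the score, true effect zero, inverse-probability weights with the score as covariate) gave .055 and .094 at SMD .19. With the baseline outcome added to Step 4, bias was −.002 and −.001.

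**3. Scored confounders that correlate with baseline.** If each of the four correlates .4 with the baseline outcome (assumed), the weighted SMD falls from .19 to about .11. The bias then falls from about .09 to about .05 at r = .5. The figures in step 2 are therefore ceilings in ordinary settings.

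**4. Baseline outcome in the score.** With a correctly specified score, simulated bias is within .002, with or without the Step 4 covariate. With a score linear in baseline when true selection is quadratic (six selection models, r = .3 and .5), bias was 0 to .018 in five models and up to .032 in the most extreme. With baseline also in Step 4 it was .005 or less in all six.

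**5. Primary outcome at 5%, baseline left out.** Prevalence per arm = 5% ∓ phi × half the baseline gap.

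- Baseline 2.9% v 7.1% (SMD .194, half-gap 2.1 points). At phi .2: 4.58% v 5.42%, OR .84. At phi .3: 4.37% v 5.63%, OR .77. The null-effect OR passes .75 only above phi ≈ .32.
- Baseline 4.0% v 6.0% (SMD .092): OR .92 and .88.

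**6. Precision.** If baseline is outside the score, adding it to Step 4 takes the SE from .0235 to .0235 × √(1 − r²): .0224 at r = .3 and .0204 at r = .5. If it is already in the score, the sampling variability of the estimate is unchanged. The reported SE falls slightly (.0213 to .0205 in one check at r = .5).

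**The case against.** The strongest reply is that the SAP already deals with this. Step 1 says that measured confounders predictive of both selection and outcome go into the score, and a baseline outcome plainly predicts its follow-up value. At this sample size an SMD of .19 is .19/.0235 ≈ 8 standard errors from zero, and .10 is about 4. With an assumed design effect of 2 these become 5.7 and 3.0. A variable that imbalanced would be recognised as predictive of selection. The larger figures arise only if the SMD sentence is read as overriding the inclusion rule, and the two can be read together. The candidate table is not supplied and may list baseline outcomes. This largely stands: entry into the score is the likely outcome.

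It is also tempting to infer that the plan tolerates a baseline-outcome imbalance of up to 0.2. It does not say so. The 0.2 limit applies after adjustment, to variables in the score; it is not an entry cut-off. The .19 used here is illustrative. At SMD .10 the bias stays below .06 for r up to .5.

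What remains is that the selection sentence has no cut-off and forces no variable in, and the balance check does not cover excluded variables. Listing baseline outcomes in the table would make them candidates, but the selection step would still apply.

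**Conclusion.** The point holds as a safeguard against one failure path and against misspecification of the score. It is worth making because it costs little.

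A reader might infer that the Aim 2a estimates will be biased because baseline outcomes are ignored. The documents do not support that: the inclusion rule points the other way, and once baseline is in a correct score the bias is about zero. A reader might also infer that Step 4 is unweighted, because it names the score only as a covariate. The SAP says inverse-probability weighting is used to adjust for confounding, and weighted and unweighted models gave the same bias in the simulation, so nothing here turns on that wording.

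If a baseline outcome were left out, the bias would be at most about .03 to .05 at SMD .10 and .06 to .10 at SMD .19, for assumed r of .3 to .5, against a stated detectable d of .06. It would be less where scored confounders correlate with baseline. The primary outcome is affected materially only if baseline perpetration is a strong predictor and the imbalance is near the upper value. Confidence is medium, because the correlations, the imbalances and the contents of the measurement table are unknown.

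**What to change.** In the Aim 2a Step 4 models, add the baseline measure of the same outcome as a covariate, whether or not it is in the propensity score. Always include baseline outcomes in the balance table, even if the selection step leaves them out of the score. Keep the propensity score, school and the classroom-clustered standard errors.

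For logistic outcomes the odds ratio then becomes conditional on baseline, while the stated target is the average treatment effect, so standardise the model predictions to report that effect. The shift is small: at 5% incidence and phi .3, a marginal OR of .75 corresponds to a conditional .73.

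Do not carry the covariate into sparse Aim 2b subgroups. In the projected gender-minority group of 181, baseline perpetration at an assumed 1% to 5% means about 2 to 9 students (181 × .01 = 1.8; 181 × .05 = 9.1), too few for a stable term.

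The cost is SAP wording, one extra term per model (a baseline latent measure where latent outcomes are used) and the standardisation step. No new data are needed, and no precision is lost in the checks above.

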ClinicalTrials.gov Data Entry Cover Sheet

Protocol ID: 22811 **Clinical Trials.gov ID:** NCT05988398

Project Title: Preventing Commercial Sexual Exploitation of Children (Project LIVE)

Principal Investigator: [name], University of Nebraska-Lincoln

Statistical Design and Power

Power Analyses

Aim 1a. N/A

Aim 1b. There is no “magic bullet” for sample size in qualitative research.¹²⁷⁻¹²⁹ The sample size proposed for focus groups is consistent with other research conducted by the PI and Co-I ([name]) that should allow for saturation (i.e., the collection of new data does not produce additional insights).¹³⁰ However, the sample size may be adjusted until data saturation is achieved.¹³⁰

Aim 1c. N/A

Aim 1d. Power analyses to support the sample size for the measurement development study (for multi-item measures) are based on prior simulation work.¹³¹ The proposed sample size of $n=878$ baseline surveys from youth will be utilized by splitting the sample in half to conduct exploratory factor analysis (EFA) and confirmatory factor analysis (CFA), each with 439 youth. A sample size of 439 youth is adequate for implementing factor analyses using structural equation modeling approaches and provides power ($> .80$) to estimate two factor models, five manifest indicators each, nonnormal data, and factor loadings = .80.

Aim 1e. Regarding qualitative data, see narrative above for Aim 1b. Also, power analyses were not conducted for descriptive data (e.g., frequencies of the number of sessions attended, extent to which sessions were delivered with fidelity). Regarding student survey data collected as part of the OPT, we will examine changes in intermediary outcomes (see Figure 1) over time given that there will likely not be a sufficient window of time to see changes in behavioral primary and secondary outcomes at the immediate post-test which will happen within a few days to a week or two following the ending of the programming. For the exploratory program impact analysis on intermediary outcomes (Figure 1), a sample size of $n=878$ (approximately .5 assignment rate to condition), will provide adequate power (.80; $\alpha=.05$) to detect a minimum effect size (MDES) $d=.20$ as determined by G-Power analysis of covariance (ANCOVA) routine.

Aim 1f. N/A

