Aim 2a. Power analyses to support the sample size for the effectiveness analyses for our primary, secondary, and intermediary outcomes (see Figure 1) were conducted using G-Power 3.1. Power was set to .80 and $\alpha=.05$. Component A of the study will provide incidence rates which will be used to recalculate power prior to the implementation of Component B. For the purposes of this proposal, we calculated the MDES based on the proposed sample size. For the primary outcome of CSEC perpetration, there are no reliable incidence estimates in the literature on which to draw. With a sample size of 7,241 students enrolled, assuming conservative minimum incidence rates of CSEC perpetration of 1% to 5% (although we hypothesize it will be higher), we have power to detect an MDES difference between conditions, odds ratio (OR)=.49 to .75, respectively. Similarly, for secondary outcomes of CSEC victimization, we estimated a range of incidence rates from a conservation 5% to 50%+ based on literature discussed following for other types of victimization^{96, 132, 133} as well as rates of CSEC youth at increased risk (e.g., system involved, homeless)¹⁸⁻²⁰, which will be present in our sample based on DMPS data, we have the power to detect an MDES difference between conditions, odds ratio (OR)=.75 to .88, respectively. For secondary outcomes of TDV/SV perpetration and victimization, given past 12- months incidence rates¹³² (from nationally representative data from youth) of 63% for perpetration (of any type of TDV) and 69% for victimization (of any type of TDV), we have power to detect an MDES difference between conditions, odds ratio (OR)=.88 to .89. For sub-types of TDV (past 12-month incidence rates: physical victimization: 18%; sexual victimization: 18%; psychological victimization: 66%; physical perpetration: 12%; sexual perpetration: 12%; psychological perpetration: 62%)¹³², we have power to detect an MDES difference between conditions, odds ratio (OR)=.83 to .89, respectively. For the secondary outcome CSEC bystander action and opportunity and intermediary outcomes (i.e., knowledge, valuing of self and others, healthy relationship skills, bystander efficacy, perceptions of school social norms, prevention conversations with school personnel), the ANCOVA routine suggested power (.80) to detect a small difference between groups (MDES $d=.06$).

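### Does Aim 2a need a rule for whether post-test, follow-up or both decides the primary outcome, CSEC perpetration?

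*SAP*

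**What the plan says.** The SAP's Outcome Analyses (Aim 2a) names "reductions in CSEC perpetration (primary outcome") as the leading hypothesis. It defines the target as the average treatment effect on the primary and secondary outcomes. The effects are then described as "differences between experimental conditions at post-test and follow-up on outcomes (for continuous measures"; the bracket closes there. The expectation follows: "At post-test and follow-up, we expect the difference between the experimental conditions to be significantly greater than zero". The next modelling sentence reads "For categorical variables, logistic regression will be used to examine differences in prevalence by condition", with no time point. Hypotheses are to be judged across several indicators (p-values, confidence intervals, standardised differences, direction of path coefficients, odds ratios), and nothing says how the two time points combine.

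Power Analyses, Aim 2a, treats CSEC perpetration as an incidence of 1% to 5%. With 7,241 students, alpha .05 and power .80, it gives detectable odds ratios of .49 to .75. No time point is attached. The SAP adds that "Component A of the study will provide incidence rates which will be used to recalculate power prior to the implementation of Component B".

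For the open pilot only (Power Analyses, Aim 1e), it says that "there will likely not be a sufficient window of time to see changes in behavioral primary and secondary outcomes at the immediate post-test". The protocol is the application for Component A, Phase I, and sets no Component B assessment times.

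**The concern.** CSEC perpetration is powered through an odds ratio, so it falls under the logistic-regression sentence, the one that names no time. The sentence that does name both times is qualified as being for continuous measures. Read strictly, the primary outcome has two candidate time points, one alpha and no rule.

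The rule matters in principle. If a significant result at either time counts as success, the error rate exceeds the per-test level. If both are needed, the chance of success can fall below .80. If the choice is left until the data are in, the more favourable time point could be picked. The planned power recalculation also seems to need a time point, because incidence depends on the period over which events are counted.

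**Working it through.** **Inputs.** From the SAP, Power Analyses, Aim 2a: N = 7,241; power .80; alpha .05 (sidedness not stated); incidence 1% and 5%; detectable OR .49 and .75. Assumed here: equal groups (the SAP gives an assignment rate of about .5 for the pilot only), correlation rho between the two test statistics from 0 to .9, and the ratio of the two effects.

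**1. The SAP's own figure.** n = 7,241/2 = 3,620.5 per group. With odds = p1/(1 − p1), p2 = OR × odds/(1 + OR × odds).

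Power = Φ{[|p1 − p2| − z√(2p̄(1 − p̄)/n)] / √([p1(1 − p1) + p2(1 − p2)]/n)}.

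- 1%, OR .49: p2 = .00493. Power is 80.6% with z = 1.645 and 70.9% with z = 1.960.
- 5%, OR .75: p2 = .03797. Power is 80.2% and 70.4%.

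Solving for exactly 80% with z = 1.645 gives OR .494 and .751, which match the SAP. The figure therefore describes one comparison (one-sided .05, no allowance for clustering). It makes no statement about two comparisons together. Sidedness is a separate matter.

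**2. If both time points are required.** Type I error cannot exceed that of a single test, so it is at most .05. With 80% power at one time point the noncentrality is z + .842, which is 2.802 two-sided. Joint power = Φ₂(.842, r × 2.802 − 1.960; rho), where r is the other time point's effect relative to the first.

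| Effect at the other time point | rho = 0 | rho = .5 | rho = .9 |
|---|---|---|---|
| three quarters as large | .445 | .503 | .552 |
| equal | .640 | .687 | .750 |
| 4/3 as large | .770 | .785 | .799 |

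At rho = 0 these are simple products. Equal: .80 × .80 = .640. At 4/3: 4/3 × 2.802 − 1.960 = 1.776, Φ = .962, and .80 × .962 = .770. At three quarters: .75 × 2.802 − 1.960 = .141, Φ = .556, and .80 × .556 = .445. On a one-sided basis the outer rows run from .470 to .581 and from .762 to .799; the equal row does not change.

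The result depends on whether the .80 is attached to the stronger or the weaker time point, and the SAP does not say.

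**3. If either time point sufficed**, each tested at .05:

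| | rho = 0 | rho = .5 | rho = .9 |
|---|---|---|---|
| any false significant result, two-sided | 1 − .95² = .0975 | .0907 | .0704 |
| false benefit, two-sided | 1 − .975² = .0494 | .0454 | .0352 |
| false benefit, one-sided .05 | 1 − .95² = .0975 | .0878 | .0681 |

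**4. Which reading the text supports.** The expectation sentence joins the two time points with an and, covers the outcomes generally, and carries no restriction to continuous measures. The logistic sentence comes straight after it and supplies the model for the other type of variable. The bracket about continuous measures is naturally read as marking the effect scale (a difference, as opposed to an odds ratio). It need not mark a different visit schedule. An analyst following the section would fit the logistic model at both times and report both.

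**The case for a change.** The best case for a change is this. The sentence is an expectation and not a success criterion. The sentence before it is limited to continuous measures. Even on the reading that both are required, the .80 does not describe the chance of meeting the primary hypothesis. Naming one time point would cost only wording and would remove a choice that could otherwise be made after seeing results. The sponsor's own remark that the pilot post-test is too early for behaviour suggests that requiring both could hide a real effect.

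The factual core stands: no rule is written in the supplied text, and an either-suffices reading would raise the error rate as shown. The rest is weaker.

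- It is not true that alpha .05 and power .80 must conflict unless the tests are almost perfectly correlated with equal effects. Both hold for each test, and joint power stays close to .80 when the unpowered time point has the larger effect.
- The SAP solved for a detectable effect at a fixed sample size, so a joint rule would show up as a different odds ratio. No number of extra students follows from it.
- The pilot text describes a baseline and an immediate post-test only, so no pilot follow-up incidence is shown among which the recalculation would have to choose.
- The remark about timing covers the pilot. The Component B post-test may or may not be as early.
- Figure 1, Table 3 and the funded proposal are not in the supplied text, and outcome timing may be set there.

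**Conclusion.** This is a gap that analysts fill sensibly. The plan compares the conditions at post-test and at follow-up and expects benefit at both. On that reading the false-positive rate for the primary conclusion is at most .05, and the published odds ratios stand as figures for a single comparison. Joint power of about 64% to 75% with equal effects, or about 77% to 80% (two-sided) if the other effect is a third larger, is a fact about a criterion for which the SAP never claimed .80. The error figures of 7.0% to 9.75% apply only if a reader adopts an either-suffices rule that the text does not state; at two-sided .05, false benefit would even then stay below 5%.

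The conclusion rests on assumed correlations of 0 to .9, equal group sizes, no allowance for clustering or weighting, and the supplied text alone. Nothing in that text settles which time point should be decisive, so a change would swap one unstated choice for another that the documents cannot support.

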Aim 2b. For the mediation analyses, based on simulation literature^{134, 135}, a sample size of 7,241 provides power ($> .80$) to detect small effects ($a=.28$; $b=.14$), which are typical of mediation designs. For the moderation analyses, we used simulation-based approach to power analysis using Mplus¹³¹. We used a multiple group model, assuming categorical moderators (e.g., gender). The proposed sample size provides sufficient power ($> .80$) to detect moderation group differences in treatment effects, $b=.20$. As an alternative way to examine power for moderation of treatment effects, we examined the MDES within moderation groups. For this analysis (G-Power ANCOVA), we took a conservative approach and used the moderator that may have the largest discrepancy in group size, such as gender identity and sexual orientation. Based on population data, we estimate 2.5% will identify as a gender minority (inclusively defined, e.g., trans, non-binary, gender queer, Two Spirit)¹³⁶⁻¹³⁸, leaving a sample size of $n=181$; and 10% of the sample will identify as a sexual minority^{113, 139}, leaving a sample size of $n=724$. Simulation power analysis supports being able to detect a small condition group difference, MDES $d=.20$.

Aim 2c. N/A

Aim 2d. N/A

Aim 2f. N/A

Proposed Analyses

Aim 1a. N/A

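### Aim 2b does not say that its mediation bootstrap resamples classrooms, and the classroom adjustment of standard errors in Aim 2a does not reach a bootstrap interval

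*SAP*

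**What the plan says.** In the SAP's Proposed Analyses, under Mediation and Moderation Analyses (Aim 2b), mediation is tested by the product of coefficients, using "bias-corrected bootstrapping with 1000 resamples to calculate the confidence intervals". The same paragraph says what its models carry: "including the propensity score and school as covariates in all models". Classroom is not mentioned there, and the resampling unit is not named.

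Classroom does appear at the end of Outcome Analyses (Aim 2a), immediately before Aim 2b: "Classroom will be used as a cluster variable to adjust the standard errors for nesting". The same sentence stands in the pilot analysis, Aim 1e. On schools, Aim 2a says: "Multilevel modeling is not possible given the small number of schools; thus, school will be included as a covariate".

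Under Power Analyses, Aim 2b, the SAP claims power above .80 for mediation with 7,241 students and paths a = .28 and b = .14. Neither document gives an ICC, a class size, a number of classrooms or the level at which condition is set for Component B. The protocol covers only the Phase I focus groups and cognitive interviews.

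**The concern.** The SAP accepts that students are nested in classrooms and deals with this by adjusting standard errors. A bootstrap interval does not use a standard error from the fitted model. Its limits are quantiles of the estimates obtained from the resampled data sets, and the bias correction only shifts which quantiles are read. If students are drawn singly, the resampled estimates vary as though students were independent, whatever adjustment is applied to the model's standard errors. Carrying the Aim 2a sentence over to Aim 2b would therefore not repair the interval. Clustering is reflected only if the resampling itself follows the classrooms.

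At stake is the explanation of how the program works. If condition is set by classroom and classmates resemble each other on a mediator such as perceived norms, the interval for the program-to-mediator path is too narrow. The report could then name a mediator that the program did not change.

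**Working it through.** **The plan's own figure.** With N = 7,241, √N = 85.09. Take SE_b = 1/√N = .01175. Reading a as a standardised mean difference under 1:1 allocation, SE_a = 2/√N = .0235. The 1:1 split is stated only for the pilot ("approximately .5 assignment rate to condition") and is assumed here, as is a two-sided α of .05.

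- b/SE_b = .14 × 85.09 = 11.9, and a/SE_a = .28 × 85.09/2 = 11.9.
- Joint-significance power = Φ(11.9 − 1.96) × Φ(11.9 − 1.96) ≈ 1.00, so the claim of more than .80 is reproduced. About 526 students would already give .80 (about 401 if a is read as a standardised path).
- With a design effect of 5 on the a path, 11.9/√5 = 5.33 and Φ(5.33 − 1.96) = .9996. Power is not the issue; interval width and false positives are.

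**False-positive rate if classrooms are ignored.** Assume that condition is constant within classroom, a = 0 and b = .14. Because b/SE_b is near 12, whether the interval excludes zero depends almost entirely on the a path. With m students per class:

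- design effect: DE = 1 + (m − 1) × ICC
- false-positive rate: 2[1 − Φ(1.96/√DE)]

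For example, with m = 25 and ICC = .05, DE = 1 + 24 × .05 = 2.20, 1.96/√2.20 = 1.32, and the rate is 18.6%.

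Two simulations of the bias-corrected bootstrap check this at 25 per class. One is a normal-theory version (4,000 runs, 1,000 resamples). The other uses raw data (290 classes, school-adjusted, 400 runs, 400–500 resamples, Monte Carlo error about 1.3–1.9 points for student resampling).

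| ICC | DE | Formula | Students resampled: normal-theory | Students resampled: raw data | Classrooms resampled: normal-theory | Classrooms resampled: raw data |
|---|---|---|---|---|---|---|
| 0 | 1.00 | 5.0% | 5.5% | 7.5% | 5.8% | 7.2% |
| .01 | 1.24 | 7.8% | 8.6% | – | 5.7% | – |
| .02 | 1.48 | 10.7% | 10.7% | – | 5.3% | – |
| .03 | 1.72 | 13.5% | 14.3% | 15.8% | 5.2% | 6.8% |
| .05 | 2.20 | 18.6% | 18.6% | 16.5% | 5.7% | 4.8% |
| .10 | 3.40 | 28.8% | 29.9% | – | 6.0% | – |

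A separate simulation with 302 classrooms of 24 (1,000 resamples, 250–300 runs) gave 11.6% at ICC .02 and 20.3% at ICC .05 when students were resampled, against 4.4% and 5.0% when classrooms were. The formula at m = 24 gives 10.5% (DE 1.46) and 18.1% (DE 2.15).

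**How far the result depends on the assumptions.**

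- Class sizes of 15–30 with ICC .01–.10: 6.6% to 32% by the formula.
- Condition varying between students within classrooms, ICC .05: 6.8% (raw data, students resampled).
- Both paths zero, ICC 0–.10: 0.6% to 3.4%.
- a = .28 with b = 0, ICC 0–.10: 5.2% to 8.5%.

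**Bias correction.** At b = .14 and ICC .05, resampling students gives 18.6% with the bias-corrected interval and 18.3% with the percentile interval. The excess comes from the ignored clustering.

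**The case against.** The strongest reply is that the SAP is silent, not wrong. It nowhere says that students will be drawn singly. It names classroom as the cluster variable twice, the second time directly before Aim 2b and under a heading shared by Aims 2a and 2b. A reader might infer that the plan has chosen a student-level bootstrap; the text does not support that. What remains is that the sentence in question concerns standard errors, so even a generous reading leaves the bootstrap interval without a classroom adjustment.

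A reader might also infer one inflated error rate for this trial. The documents cannot support that either, since the ICC, class size and level of assignment are all assumed here. Classroom-level assignment is plausible: school indicators can sit beside condition in a model only if condition varies within schools, and classroom is the only smaller unit the SAP names. But this is not stated, and the propensity model is written for each student. The larger figures also apply to one null only, where the program leaves the mediator unchanged and the mediator predicts the outcome.

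The simulations leave out propensity weighting, missing data, latent variables and binary outcomes. School covariates would absorb any between-school part of the clustering, so the relevant ICC is what remains within school. These points limit the size claimed but do not remove the gap.

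**Conclusion.** The point holds as a gap with a definite consequence: run as an ordinary student-level bootstrap, the Aim 2b mediation analysis would ignore nesting that the SAP itself recognises. With condition set by classroom, 24–25 students per class, a = 0 and b = .14, the nominal 5% rate becomes about 9% at ICC .01, 11–12% at .02, 19–20% at .05 (16.5% in the smaller raw-data simulation) and about 30% at .10. There is little or no excess if condition varies within classrooms or if both paths are zero.

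The point does not extend to the Aim 2a effectiveness analyses, which have a stated classroom adjustment, or to the mediation power claim. It is also no argument against the bias-corrected interval as such.

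**What to change.** Add to Aim 2b: *Confidence intervals for indirect effects use a bootstrap that resamples whole classrooms (or another classroom-cluster-robust interval for the product of coefficients).* It would help to state in the same place the level at which condition is set.

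The bias-corrected form can stay. Changing to percentile limits, or re-estimating the propensity score in each resample, is optional and not needed for this correction. The cost is more computing time and wider intervals. At the planned path sizes, power stays above .99 even with a design effect of 5.
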